9.3.3 Exploratory Hypothesis

There are no exploratory hypotheses.

9.4 Sample Size Determination

This is a non-inferiority study, and the sample size calculation was based on a non-inferiority test for SRT (Speech Recognition Threshold) scores (Kanso 3 Sound Processor with SCAN 2 FF compared to Kanso 3 Sound Processor with SCAN 2 (ForwardFocus OFF) in 65 dB SPL SONrearhalf 4TB).

To reject the null hypothesis of inferior sentence in noise scores (SRT scores), the following parameters were chosen for sample size calculation:

- A non-inferiority margin of 1 dB SRT. This margin is based on clinical consensus. NB: *higher SRT scores represent poorer performance*.

- A standard deviation (SD) of 1.36 dB for the difference (in scores). This SD is calculated from 256 paired differences and is an indicative test re-test SD for both SONrearhalf and SON3.
- A significance level $\alpha = 0.025$ (one-tailed).
- A desired power of 0.8.

Based on these assumptions, a sample size of 17 is required to reject the null hypotheses of inferiority using a confidence interval method (one-tailed 97.5% confidence interval). Allowing for up to 15% attrition, a sample size of 20 subjects is planned for this study.

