4.2.2.2 Clinical Data for OTE Sound Processors

The main relevant study with an OTE Sound Processor is the CLTD5754 study, the primary objective of this study was to determine the feasibility of ForwardFocus in an OTE configuration and the secondary objective was to collect formative usability information with prototype and early design versions of the Kanso 2 (CP1150) Sound Processor.

Twenty-two adult subjects underwent speech perception testing using Australian Speech Test In Noise (AuSTIN) adaptive sentences presented from the front with 4 talker babble noise from 90,180 & 270 degrees to the subject (SON3). AuSTIN Speech Reception Threshold (SRT) data comparing ForwardFocus ON and ForwardFocus OFF demonstrated superiority with ForwardFocus ON ($P=0.002$, paired t-test).

The implementation of ForwardFocus in the CLTD5754 included the fixed microphone directionality Zoom and no automation. This evidence supported the approval of ForwardFocus with the Kanso 2 Sound Processor.

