7.2.3 Number of Subjects Required

A total of twenty subjects are to be recruited to meet the sample size calculation requirements (Section 9.4) with a dropout rate of no more than 15%.

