7.3.2.1 Speech perception in noise

Speech perception in noise will be measured using the Australian Speech Test In Noise (AUSTIN) (Dawson, Hersbach, & Swanson, 2013), which is a test that uses BKB like target sentences presented in adaptive noise. The goal of the speech perception test in noise is to provide the SNR for 50% speech intelligibility. The signal level will be fixed at 65 dB SPL. Sentence in noise tests will be measured using this procedure in the two speaker configurations shown below.

[figure not shown]

Figure 3. Left – SON3 with babble noise from 90, 180 and 270 degrees (3 talkers in total). Right -SONrearhalf with roving babble noise presented from 4 speakers in the rear hemisphere (4 talkers in total). The rear hemisphere will consist of 7 speakers and the 4 noise speakers will change for every sentence in the test list.

In booth speech perception testing will be conducted using the signal processing combinations and hardware listed in Table 2. The order of testing will be conducted according to the counterbalancing outlined in Section 7.2.7.

Table 2. Speech in Noise test conditions (SONrearhalf and SON3). Whisper, WNR, ADRO and ASC will be activated according to user preference.

#	Condition	SNR-NR	Sound Processing	Directionality	ForwardFocus	Comparisons
1	Kanso 3 SCAN 2 FF Zoom (Automated ForwardFocus ON)	✓	SCAN 2	Zoom	ON	Primary: 1 vs 3 in 65 dB SPL SONrearhalf 4TB. Secondary (1): 1 vs 3 in 65 dB SPL SON3 Babble. Exploratory (2): 1 vs 2 in 65 dB SPL SONrearhalf 4TB. Exploratory (3): 1 vs 2 in SON3 Babble
2	Kanso 3 SCAN 2 FF Beam (Automated ForwardFocus ON)	✓	SCAN 2	Beam	ON	
3	Kanso 3 SCAN 2 (ForwardFocus OFF)	✓	SCAN 2	Beam	OFF	

For SONrearhalf and SON3 speech in noise tests, all subjects will be tested unilaterally. That is, unilateral subjects will have their contralateral ear (non-test ear) blocked with an earplug for all test conditions. Subjects with bilateral implants will be tested using the subject's preferred listening ear or if the preferred ear is not known then the first implanted ear will be used as the test-ear.

The subject will be positioned so that the middle-point of two ears is centred at the reference point of the sound field. The loudspeaker should be positioned at the same height as the middle-point of the two ears.

The AuSTIN software will be used to present the test material. The investigator, or suitably qualified delegate will use the software to select:

- Adaptive test (SRT)

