9.5 Analysis Populations

This study has a non-inferiority design; therefore, the primary endpoint analysis will be based on the Per Protocol population (PP).

For cases in which the Intent-to-Treat (ITT) and PP populations lead to the same conclusions and interpretations about the treatment effect, the results will be considered to not be influenced by underlying factors such as missing data and protocol deviations, and the results would be considered to be robust and consistent under different analysis populations. A statement to reflect this will be included in the Clinical Investigation Report.

For cases in which the ITT and PP populations lead to different final conclusions or interpretations, the results will be reported for both analysis sets and the differences in outcomes will be identified and explored.

Intent-to-Treat Population

The ITT Population will include all subjects who consented and participated (refer Section 7.2.5).

For the purposes of the analyses of the primary and secondary endpoints, subjects will be included in the analysis regardless of protocol deviations. Missing data will not be imputed. Consequently, only subjects with paired treatment and control measurements will contribute to the analysis.

Per Protocol Population

The PP will include all subjects who have one set of paired measurements from treatment and control (for speech outcomes or SSQ12), without major protocol deviations. Major deviations will be defined at the clean file meeting before database lock. Treatment administration not conducted in the intended counterbalanced order of presentation will also be regarded as a protocol violation. However, it is expected that the sequence and period effects are minimal in this study, if any.

This analysis set will be the primary analysis set for the testing of non-inferiority (primary and secondary hypotheses).

Safety Population

The Safety Population will include all treated subjects. The Safety Population will be used for the safety data analysis.

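### Does Section 9.4's 80% power fail because it uses a test-retest SD, leaves the true difference unstated and does not tie 17 to the per-protocol set?

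*Combined protocol and SAP*

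**What the plan says.** Section 9.4 of the combined protocol and SAP bases the sample size on a paired non-inferiority test of the speech reception threshold with noise from the rear half. The listed inputs are a 1 dB margin, an SD of 1.36 dB for the difference in scores, one-sided alpha 0.025 and power 0.8. On the SD it states: "This SD is calculated from 256 paired differences and is an indicative test re-test SD for both SONrearhalf and SON3". The result is 17 subjects, and then: "Allowing for up to 15% attrition, a sample size of 20 subjects is planned for this study". Section 7.2.3 repeats the allowance, "with a dropout rate of no more than 15" per cent. No assumed true difference is given.

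The comparison being powered is defined in Section 7.3.2.1, Table 2: "Primary: 1 vs 3 in 65 dB SPL SONrearhalf 4TB". Condition 1 is Zoom with ForwardFocus on; condition 3 is Beam with ForwardFocus off.

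Section 9.5 says that "the primary endpoint analysis will be based on the Per Protocol population (PP"), that major deviations are settled at the clean file meeting, and that "Treatment administration not conducted in the intended counterbalanced order of presentation will also be regarded as a protocol violation". Section 7.2.6 rules out replacing withdrawn participants.

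On the likely direction of the effect, Section 4.2.2.2 reports for the 22-subject off-the-ear study: "AuSTIN Speech Reception Threshold (SRT) data comparing ForwardFocus ON and ForwardFocus OFF demonstrated superiority with ForwardFocus ON" (P=0.002, paired t-test). It adds the limitation that "The implementation of ForwardFocus in the CLTD5754 included the fixed microphone directionality Zoom and no automation". Section 4.2.2.1 reports ForwardFocus superior with rear babble in studies on behind-the-ear processors.

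**The concern.** A test-retest SD, in the usual sense, describes how much a score moves when the same person repeats the same test. The primary contrast is between two different programs. If some recipients gain more from ForwardFocus than others, the paired difference varies by that amount as well, and 1.36 dB would understate its SD. Section 9.4 does not name the study or the number of subjects behind the 256 differences, so the substitution cannot be checked.

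The other two conditions look equally tight. Without a stated true difference, a reader has to solve backwards for a core input. The 15% is described only as attrition, while the primary analysis set can also lose subjects to protocol deviations. Since 20 × 0.85 is exactly 17, nothing is left over for a fourth loss from any cause.

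What would be at stake is type II error: a study described as having 80% power might have less, and a failure to show non-inferiority would be hard to interpret.

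**Working it through.** **Method.** Paired non-inferiority t-test, matching the t-based intervals of Section 9.1. Power = P(T > t[0.975, n−1]), where T is noncentral t with n−1 degrees of freedom and noncentrality (1 − δ)·√n / SD. Here δ is the true ON-minus-OFF difference in dB; negative δ is a benefit.

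**1. The plan's own figure.** With SD 1.36 and δ = 0:
- n = 16: noncentrality √16/1.36 = 2.94, power 78.5%.
- n = 17: noncentrality √17/1.36 = 3.03, power 81.2%.

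So 17 is the smallest n reaching 80%. Then 17/0.85 = 20. Both figures reproduce, and the unstated δ is recoverable: at n = 17, power drops below 80% once δ exceeds +0.016 dB, so zero was evidently used.

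**2. Size of the per-protocol set** (SD 1.36, δ = 0).

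| n | 20 | 18 | 17 | 16 | 15 | 14 |
|---|---|---|---|---|---|---|
| Power | 88% | 84% | 81% | 78% | 75% | 72% |

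A fourth loss costs under three percentage points; six losses cost nine.

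**3. A larger SD with no mean benefit.** Let τ be the SD of true between-subject variation in program effect. Total SD = √(1.36² + τ²). The documents give no τ; these values are assumptions.

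| Assumed τ (dB) | Total SD (dB) | Power, n = 17 | Power, n = 20 |
|---|---|---|---|
| 0.5 | 1.45 | 76% | 83% |
| 1.0 | 1.69 | 63% | 71% |
| 1.36 | 1.92 | 52% | 60% |

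The largest total SD that keeps 80% at δ = 0 is 1.38 dB for n = 17 and 1.51 dB for n = 20.

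**4. The same SDs with a mean benefit.** The benefit that restores 80% at n = 17 is 0.05, 0.22 and 0.39 dB for the three rows above. With a 0.5 dB benefit, power stays at or above 80% up to a total SD of 2.07 dB.

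**5. What the cited off-the-ear study implies.** Assume all 22 subjects were analysed and P = 0.002 is two-sided. Then t(21) = 3.527, and mean/SD = 3.527/√22 = 0.75, with a noncentral-t 95% interval of 0.27 to 1.22. If that ratio carried over, the noncentrality at n = 17 would be √17·(1/SD + ratio):
- Ratio 0.75: power is at least 82.9% whatever the SD, because √17 × 0.75 alone delivers that much.
- Ratio 0.27, the lower limit: power is 96%, 92% and 86% at total SDs of 1.45, 1.69 and 1.92, and stays at or above 80% up to 2.20 dB.

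**6. Direction of the SD error.** Variation in program effect would push the SD above 1.36. Section 7.3.4 requires all conditions for one endpoint to be tested on the same day. If the 256 differences came from separate sessions, which the documents do not say, 1.36 would include session-to-session variance that this study avoids. The net direction cannot be settled from the documents.

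**The case for a change.** The best case for acting is that Section 9.4 should carry its own justification. At a true difference of zero the headroom is only 0.02 dB of SD at n = 17, and even with all 20 subjects analysed an assumed τ of 1.0 dB gives 71%. The reassurance from the earlier study is indirect: it used the other noise configuration (babble from 90, 180 and 270 degrees), fixed Zoom, no automation and early versions of the previous processor, and its standardised benefit has a wide interval. If the sponsor is relying on an expected benefit, the plan could say so. The remedy would be cheap: a few sentences and perhaps a power table.

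Much of this is fair. The use of a retest SD for a between-program contrast is not justified in the text, and the true difference is not stated. But the low power figures require two unfavourable assumptions together, a sizeable τ found nowhere in the documents and a mean benefit of zero, while the only directional evidence the documents give favours ForwardFocus with spatially separated babble. Nor is the SD concealed: it is openly labelled indicative and test-retest. The link to the per-protocol set follows from reading Sections 9.4 and 9.5 together, since 17 is the number needed to reject the null and the per-protocol set is where that test is made. Whether a test-order deviation removes a subject is a question about the population definition in Section 9.5, not about the sample size.

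**Conclusion.** No change follows. The stated 17 and 20 are correct for a 1 dB margin, SD 1.36 dB, one-sided alpha 0.025 and a true difference of 0 dB, the usual default and the value that reproduces the result. What is missing is supporting detail: where the 256 differences come from, why their SD suits the ON-versus-OFF contrast, and an explicit statement that 17 counts per-protocol subjects.

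The documents do not establish that power is below 80%. At zero benefit and n = 17 it would be 76%, 63% or 52% for assumed τ of 0.5, 1.0 or 1.36 dB. With the lower-limit standardised benefit from the off-the-ear study it would be 96%, 92% or 86%. The latter range assumes that a study in another configuration and on an earlier device is a fair proxy.

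Supplying the detail would not alter the trial. The change history in Section 25 records that all subjects had been recruited by the version 3 amendment, so N is fixed. Type I error, the t-based interval and the comparison of its upper limit with 1 dB (Section 9.6.1) use the observed SD, not the planning value. The width of that interval will show the precision actually achieved, which is what a reader needs if non-inferiority is not shown.

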9.5 Analysis Populations

This study has a non-inferiority design; therefore, the primary endpoint analysis will be based on the Per Protocol population (PP).

For cases in which the Intent-to-Treat (ITT) and PP populations lead to the same conclusions and interpretations about the treatment effect, the results will be considered to not be influenced by underlying factors such as missing data and protocol deviations, and the results would be considered to be robust and consistent under different analysis populations. A statement to reflect this will be included in the Clinical Investigation Report.

For cases in which the ITT and PP populations lead to different final conclusions or interpretations, the results will be reported for both analysis sets and the differences in outcomes will be identified and explored.

Intent-to-Treat Population

The ITT Population will include all subjects who consented and participated (refer Section 7.2.5).

For the purposes of the analyses of the primary and secondary endpoints, subjects will be included in the analysis regardless of protocol deviations. Missing data will not be imputed. Consequently, only subjects with paired treatment and control measurements will contribute to the analysis.

Per Protocol Population

The PP will include all subjects who have one set of paired measurements from treatment and control (for speech outcomes or SSQ12), without major protocol deviations. Major deviations will be defined at the clean file meeting before database lock. Treatment administration not conducted in the intended counterbalanced order of presentation will also be regarded as a protocol violation. However, it is expected that the sequence and period effects are minimal in this study, if any.

This analysis set will be the primary analysis set for the testing of non-inferiority (primary and secondary hypotheses).

Safety Population

The Safety Population will include all treated subjects. The Safety Population will be used for the safety data analysis.

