To compare adult cochlear implant speech perception in spatially separated speech and noise (AuSTIN, 65 dB SPL SON3 Babble) between CP1170 microphone directionalities, SCAN 2 FF Zoom (Automated ForwardFocus ON) and SCAN 2 FF Beam (Automated ForwardFocus ON).	Paired difference in dB SRT (AuSTIN, 65 dB SPL SON3 Babble) between the CP1170 SCAN 2 FF Zoom (Automated ForwardFocus ON) and CP1170 SCAN 2 FF Beam (Automated ForwardFocus ON).
To compare subjective acceptance and satisfaction between microphone directionalities: CP1170 sound processor using SCAN 2 FF Zoom and CP1170 sound processor using SCAN 2 FF Beam.	Ratings based on the CP1170 Questionnaire after a minimum 2-weeks actual-use of the CP1170 sound processor SCAN 2 FF Zoom and CP1170 sound processor SCAN 2 FF Beam.

3 Schedule of Events

Visit Type	Screening	Visit 1 ^a	Visit 2 ^b	Ad Hoc ^c	EOS ^d
Timing of Investigation	Day 0	Day 0	Week 2	NA	Month 12
Visit window (±)	NA	+ 7 days	+ 14 days	NA	± 30 days
Written informed consent	X				
Demographics	X				
Eligibility	X				
Hearing history	X				
Device history	X				
Medical history	X				
Baseline Questionnaire ^e		X			
SSQ12 - Own Processor ^f		X			
SSQ12 - CP1170 Sound Processor ^g				X	
APHAB Questionnaire				X	
CP1170 Fitting ^h		X		X	
Fitting optimisation ⁱ			X	X	
Speech perception testing - Speech in Noise ^{jk}				X	
Speech perception testing – Words in Quiet ^l				X	

^a Screening and visit 1 may occur on the same day.

^b Visit 2 signifies the end of the first take-home period. Procedures from Ad Hoc visits may be performed on the same day as required.

^c Ad Hoc refers to any unscheduled visit and may be repeated.

^d EOS can occur on the same day as an Ad Hoc visit.

^e Information regarding the subject's own sound processor, i.e. that which they had been using prior to screening, and usage habits.

^f Own processor is defined as the sound processor that the subject used for a minimum of 2 weeks prior to their enrolment.

^g SSQ12 on the IMD following the final take-home period.

^h First fitting of the investigational sound processor.

ⁱ Fitting optimisation is subject to need and may include programming changes, and hardware or firmware modifications or updates to the investigational sound processor.

^j In-booth testing CP1170 SCAN 2 ForwardFocus ON compared with the CP1170 ForwardFocus OFF (65 dB SPL S0Nrearhalf 4-talker babble).

^k CP1170 ForwardFocus ON (SCAN 2) and ForwardFocus OFF (SCAN 2) (65 dB SPL S0N3 babble).

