7.2.6 Criteria and Procedures for Subject Withdrawal

Subjects can decide to withdraw from the investigation at any time. The Investigator shall ask the reason(s), however subjects have the right to withhold their reason if preferred. The reason for withdrawal should be documented in the subject's source files and the electronic case report form (eCRF), if provided.

The Investigator or Sponsor may also decide to withdraw a subject from the clinical investigation or stop the use of the investigational device if it is considered to be in the subject's best interests.

Subject withdrawal may be for any of the following reasons:

- Adverse Event (AE)
- Device Deficiency (DD)
- CIP or GCP deviation
- Subject withdrew consent
- Subject lost to follow-up
- Subject death
- Sponsor decision
- Investigator decision
- Other (specify)

If a subject is lost to follow-up, every possible effort must be made by the study site personnel to contact the subject and determine the reason for discontinuation. At least 3 separate attempts taken to contact the subject must be documented.

Participating subjects who are withdrawn/discontinued will not be replaced.

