- Speech perception: Speech perception testing can only be conducted in-clinic. If restrictions are ongoing at the planned time of these study visits, these tests may be moved to later in the study. As such, speech perception tests have been decoupled from specific visits and are repeatable as part of the Ad Hoc visit(s). If time permits, and study subjects are willing, all speech perception tests may be conducted on the same day. All comparisons for a specific endpoint test will be completed on the same day.

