9.6.1 Primary Endpoint Analyses

For the non-inferiority test of SRT sentence scores (Kanso 3 with SCAN 2 FF ON versus Kanso 3 with SCAN 2 (ForwardFocus OFF) in 65 dB SPL SONrearhalf 4TB), the 95% CI (alpha=0.025 one-sided) for the mean paired difference will be estimated. If the upper limit of the 95% CI of the mean paired difference is below 1 dB, the treatment condition is regarded as non-inferior to the control in terms of SRT sentence perception. The non-inferiority margin of 1 dB for SRT is based on clinical consensus.

The primary testing of non-inferiority will be conducted for the PP analysis set. If non-inferiority is demonstrated, the testing will proceed to a test of superiority in the ITT analysis set.

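### Agreement between ITT and PP cannot show that missing data had no influence, because subjects without a pair are in neither analysis

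*Combined protocol and SAP*

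**What the plan says.** Section 9.5 makes PP the primary set for non-inferiority and sets out how to read a comparison with ITT. If the two lead to the same conclusions, "the results will be considered to not be influenced by underlying factors such as missing data and protocol deviations", and the results are also to be called robust and consistent across populations. The section adds: "A statement to reflect this will be included in the Clinical Investigation Report".

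The same section then defines the two sets:

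- **ITT:** all subjects who consented and participated, kept regardless of deviations and without imputation. As a result, "only subjects with paired treatment and control measurements will contribute to the analysis".
- **PP:** "The PP will include all subjects who have one set of paired measurements from treatment and control", provided there are no major protocol deviations. Testing out of the planned counterbalanced order also counts as a violation.

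Section 9.1 repeats that nothing is imputed and plans a summary of disposition with withdrawal reasons. Section 7.2.6 states: "Participating subjects who are withdrawn/discontinued will not be replaced". Section 9.6.1 adds that, once non-inferiority is shown, "the testing will proceed to a test of superiority in the ITT analysis set"; Section 9.6.2 has the same step for the secondary endpoints. No sensitivity analysis for missing data is described.

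**The concern.** Comparing ITT with PP tells you something about missing data only if subjects with missing outcomes enter one of the two analyses. Here they enter neither. Agreement is informative about deviations and silent about the subjects whose values are unknown. The report would still carry a pre-written statement that missing data had no influence.

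Exposure differs by endpoint. For SSQ12, the own-processor score is taken at Visit 1 and, according to the Schedule of Events in Section 3, the second is "SSQ12 on the IMD following the final take-home period". A subject who leaves in between because of the device can lose the pair for a reason connected with the outcome; Section 7.2.6 lists adverse events and device deficiencies among the withdrawal reasons. The primary endpoint is less exposed. Both programs run on one device, and Section 7.3.4 says "All comparisons for a specific endpoint test will be completed on the same day".

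**Working it through.** **Step 1: the sets.** For any one endpoint:

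- analysed ITT = subjects with a pair;
- analysed PP = subjects with a pair and no major deviation;
- ITT minus PP = subjects with a pair and a major deviation;
- subjects without a pair: in neither set.

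If there are no major deviations, ITT minus PP is empty and the two results are identical, whatever the missing values would have been.

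**Step 2: the plan's own figures.** Inputs from Section 9.4: margin 1 dB, SD of the paired difference 1.36 dB, one-sided alpha 0.025, power 0.80. A true difference of 0 is not stated and is assumed here. The exact paired t-test has power 0.785 at n = 16 and 0.812 at n = 17, so 17 are needed. 17/0.85 = 20. Both stated figures reproduce. The 15% allowance means up to 3 of 20 subjects without a pair.

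**Step 3: tipping points, primary endpoint.** Take n observed pairs with mean m and SD s = 1.36, and set the k = 20 − n missing subjects to a constant c:

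- M = (n·m + k·c)/20
- SS = (n − 1)s² + n(m − M)² + k(c − M)²
- upper limit = M + 2.093 × √(SS/19)/√20

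Solve for the c at which the upper limit equals 1 dB.

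Worked case, k = 3 and m = 0. On the 17 pairs the upper limit is 2.120 × 1.36/√17 = 0.70 dB, so non-inferiority is concluded. With c = 2.10:

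- M = 6.30/20 = 0.315
- SS = 16 × 1.36² + 17 × 0.315² + 3 × 1.785² = 29.59 + 1.69 + 9.56 = 40.84
- SD = √(40.84/19) = 1.466
- upper limit = 0.315 + 2.093 × 1.466/√20 = 1.00 dB

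Mean in the missing subjects (dB) at which non-inferiority is lost; k and m are assumptions:

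| Missing | m = −1 | m = −0.5 | m = 0 | m = +0.2 |
|---|---|---|---|---|
| 3 | 4.72 | 3.50 | 2.10 | 1.40 |
| 2 | 6.56 | 4.79 | 2.77 | 1.77 |
| 1 | 11.0 | 7.93 | 4.47 | 2.73 |

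If the 3 missing values also vary with SD 1.36, the 2.10 becomes about 1.97.

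**Step 4: SSQ12.** Same formula with the sign reversed and margin −1 (Section 9.3.2). The documents give no SD, so 1.0 to 1.75 is assumed, with 3 missing. Mean in the missing subjects at which the lower limit reaches −1:

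| Assumed SD | m = 0 | m = +0.5 |
|---|---|---|
| 1.0 | −2.57 | −3.81 |
| 1.25 | −2.26 | −3.60 |
| 1.5 | −1.87 | −3.35 |
| 1.75 | −1.40 | −3.05 |

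At SD 2.0 and m = 0 the 17 pairs already fail (lower limit −1.03).

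**Step 5: why a single fill at the margin does not help.** With k = 3, m = 0 and c = 1, the SD falls from 1.36 to 1.30 and the upper limit moves only from 0.70 to 0.76 dB.

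**The case against.** The strongest reply is about weight. The pairs-only rule is stated openly, and no success rule depends on ITT/PP agreement. Sections 9.1 and 9.6 already call for numbers of non-missing observations, subject listings and withdrawal reasons, so the count of missing pairs can be read from planned output. The primary endpoint is hard to overturn. Withdrawal before testing removes both measurements and does not obviously favour either program, and the earlier studies in Section 4.2.2 found ForwardFocus better in rear or spatially separated babble, though on other devices and implementations. At an observed mean of −1 dB, even 3 missing subjects would have to average +4.7 dB.

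For SSQ12, losing the pair after early exit is not certain. Section 7.3.2.5 allows a take-home period to be paused, Section 7.3.2.6.1 asks only for completion after take-home use, and the Schedule places the questionnaire at repeatable Ad Hoc visits. The SSQ12 figures also rest on assumed SDs.

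All of this stands, and it limits the practical size of the problem. It also means that per-endpoint counts are largely in place and that relabelling the ITT superiority set is a clarification only. None of it makes the inference in 9.5 valid: disclosing who is left out does not turn a comparison that omits them into evidence about them.

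Two finer readings do not rescue it either. The PP wording might mean a pair on any endpoint, but an endpoint's difference still needs that endpoint's own pair. An omitted assessment is a deviation under Section 13 and might remove a paired subject from PP, but it never restores an unpaired one.

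**Conclusion.** The concern holds. On the plan's own definitions, ITT/PP agreement carries no information about subjects with missing pairs, yet 9.5 tells the report to read it as if it did. This follows from the definitions and needs no assumption.

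The possible effect on a conclusion does rest on assumptions. The primary result is fragile only with several missing subjects and an observed mean near or above 0. For SSQ12, with 3 missing and an observed mean of 0, the missing subjects would have to average between −2.6 and −1.4 across the assumed SDs. In every such case without major deviations, ITT and PP would still agree. Alpha, margins and sample size need no change. This should be corrected before the analysis is finalised, but it does not threaten the design.

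**What to change.** 1. In Section 9.5, remove missing data from the inference so that ITT/PP agreement is read as evidence about protocol deviations only.
2. For each endpoint, report the participating subjects without a pair and the reasons. Most of this is already planned; the new part is the reason when a subject did not withdraw.
3. Add a tipping-point table for the primary endpoint and the secondary endpoints with a non-inferiority hypothesis, on all participating subjects, showing the value in the missing subjects at which non-inferiority is lost. Do not substitute a single fill at the margin.
4. For clarity, describe the set for the superiority tests in 9.6.1 and 9.6.2 as participating subjects with paired data.

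The cost is one phrase deleted, one label changed and a small table, with no new data. The report can no longer claim robustness to missing data automatically.
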